## **4.0 EFFECTIVENESS AND SAFETY ENDPOINTS**

All effectiveness and safety endpoints based on primary heart graft dysfunction (PGD) results and the patient graft failure will use the Clinical Events Committee (CEC) adjudicated results.

### **4.1 Primary Effectiveness Endpoint**

The primary effectiveness endpoint is patient survival assessed at the six months post-transplant follow-up visit (nominal visit).

### **4.2 Secondary Effectiveness Endpoint**

The primary analysis of the secondary effectiveness endpoint is the utilization rate based on the OCS Heart Population, which is defined as the number of eligible DCD donor hearts that met the warm ischemic time (WIT) limit ( $\leq 30$  mins) and were instrumented on the OCS Heart System that meet the acceptance criteria for transplantation after OCS Heart preservation divided by the total number of eligible DCD donor hearts that met the warm ischemic time limit above and were instrumented on the OCS Heart System.

The utilization rate based on the modified OCS (mOCS) Heart Population is defined as the number of DCD hearts that were successfully transplanted after preservation and assessment on the OCS divided by total number of DCD donor hearts that were instrumented on the OCS.

### **4.3 Other Endpoints**

Other endpoints collected for the DCD heart transplanted subjects only include:

- Use of post-transplant MCS (including LVAD, RVAD, BiVAD, ECMO, TAH, IABP) for  $> 72$  hours immediately post-transplant (i.e., use initiated within 24 hours after OR discharge).

Other endpoints collected for both the DCD heart transplanted recipients and the SOC heart transplanted recipients (SOC1+SOC2) are as follows:

- Patient and graft survival at 30 days post-transplant.
- Patient and graft survival at 30 days or initial hospital discharge, if later than 30 days.
- ISHLT moderate-severe PGD (left or right ventricle) (not including rejection or cardiac tamponade) within 24 hours according to ISHLT consensus manuscript (as defined in Appendix 1 of the protocol) for both OCS and SOC patients.
- ISHLT Severe PGD (left or right ventricle) (not including rejection or cardiac tamponade) within 24 hours according to ISHLT consensus manuscript (as defined in Appendix 1 of the protocol).
- Patient survival assessed at the 12 months post-transplant follow-up visit.
- Patient and graft survival at 30, 180, and 365 days post-transplant estimated by Kaplan Meier method.

#### **4.4 Safety Endpoint**

The safety endpoint is defined as the incidence of Heart Graft-Related Serious Adverse Events (HGRSAEs) in the first 30 days post-heart transplantation, defined as:

- Moderate or Severe heart PGD (left or right ventricle) (not including rejection or cardiac tamponade) according to ISHLT consensus manuscript (as defined in Appendix 1 of the protocol).
- Primary graft failure requiring re-transplantation.

This endpoint is collected for both the DCD heart transplanted recipients and the SOC heart transplanted recipients (SOC1+SOC2).

## **5.0 STATISTICAL CONSIDERATIONS**

### **5.1 General Methodology**

All statistical analyses will be performed using SAS® Version 9.4. For the most part, the summary tables will be by analysis population [DCD Heart Transplanted Recipient Population, DCD modified-Intent-to-Treat Heart Transplanted Recipient Population, SOC Heart Transplanted Recipient Population (SOC1, SOC2, and Total) and/or SOC modified-Intent-to-Treat Heart Transplanted Recipient Population (SOC1, SOC2, and Total)]. The summaries of the secondary effectiveness endpoint (the utilization rate), and device malfunction will be produced for the OCS Heart Population and the modified OCS Heart Population.

Continuous variables will be summarized using descriptive statistics, specifically the mean, median, standard deviation (SD), minimum and maximum. Categorical variables will be summarized using frequencies and percentages.

### **5.2 Adjustments for Covariates**

The analysis of the primary effectiveness endpoint will be performed using a linear probability model with terms for treatment and the known donor and recipient risk factors for mortality listed in Section 12.1.

### **5.3 Handling of Dropouts and Missing Data**

No imputation of missing data for trial subjects will be performed for any effectiveness or safety outcome.

An AE will be considered treatment emergent unless it can be unequivocally determined (from the partial onset date and/or a partial or complete stop date) that the event occurred prior to transplantation.

For duration of ICU stay calculation, the date time of the clinical order of discharge will be used. If the clinical order of discharge date is not available, the actual discharge date will be used. Missing ICU admission time will be imputed as 00:00, and missing ICU discharge time will be imputed as 23:59. If the imputed clinical order of discharge date time is after the actual discharge, the actual discharge date time will be used for calculation.

For duration of post-transplant MCS calculation, missing support start time will be imputed as 00:00, and missing support end time will be imputed as 23:59. If the imputed MCS start time is before the OR discharge, the OR discharge time will be used as the starting point for the duration calculation.

### **5.4 Interim Analyses and Data Monitoring**

No interim analyses will be performed. The study database will have a database lock for the Premarket Approval (PMA) when all transplanted subjects either complete the Month 6 visit assessments or discontinue the study prematurely. Once all DCD patients complete Month 12 visit or discontinue the study, the additional data cut will be provided for FDA submission.

## **5.5 Multicenter Studies**

Subjects will be recruited from up to 25 sites. The effect of site and the treatment by site interaction will be tested via logistic regression. The Wald Type III p-value for site and the treatment by site interaction term will be presented.

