**Figure 1: DCD Heart Trial Design**

The trial will be conducted at a maximum of 25 participating sites with 90 transplanted DCD heart recipients and 90 SOC heart transplant recipients. Follow-up data for the SOC recipients will be obtained from the UNOS/OPTN standard database for U.S. transplant recipients through five years after transplantation.

Subjects who receive a DCD heart transplant will be followed for 12 months from the date of transplantation. Data from UNOS/OPTN transplantation database will be obtained through five years after transplant.

The Schedule of Clinical Assessments for the donor and recipient is provided in Table 1.

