### **3.5 Changes to the Protocol-Specified Analyses**

The protocol proposed stopping enrollment once the DCD heart transplanted recipients enrollment target (N=90) was met. Further, if the enrollment target in the SOC heart transplanted recipient population had not been met, a propensity-score-matched subset of subjects from the UNOS database was proposed to supplement the set of subjects in the SOC Heart Transplanted Recipient Population at the time of the last DCD transplant. However, in communications with FDA it became clear that FDA strongly preferred prospective enrollment of 90 SOC subjects rather than the propensity matched approach outlined in the protocol. Therefore, the statistical analysis will be performed using the 90 DCD and 90 SOC subjects that were prospectively enrolled without propensity-matched subjects from UNOS.

The protocol stated that the analysis of the primary effectiveness endpoint would be adjusted for known donor and recipient risk factors (defined in section 12.1) for mortality, and any of the baseline and demographic characteristics identified as potential risk factors for which there is a statistically significant difference between the treatment groups. This SAP clarifies that the primary effectiveness analysis will be adjusted for known donor and recipient risk factors for mortality, but not for baseline and demographic characteristics identified as potential risk factors.

The protocol stated that statistical testing will be performed for the comparisons of recipient demographics and baseline characteristics and of patient survival at 6 months for the following groups: SOC1 vs SOC2, DCD Heart vs SOC1, DCD Heart vs SOC2. Only summary statistics will be provided for those comparisons.

[figure not shown]

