**Figure 2. Inclusion of IABP in Post-transplant (Post-Tx) MCS Analysis**

Primary Graft Dysfunction (PGD) data for SOC patients (SOC1+ SOC2) will be collected from the investigational sites and adjudicated by CEC according to the ISHLT criteria. The ISHLT PGD will be summarized for the SOC patients based on CEC adjudication and will be compared to the DCD heart transplanted patients using descriptive statistics.

The patient survival, graft survival and hospital discharge information will be collected for SOC patients from the UNOS/OPTN database. The graft survival of SOC patients will be analyzed following CEC adjudication. Per the UNOS/OPTN Heart TRR form, graft failure includes heart re-transplantation and the cardiac-graft related death. Deaths that are a result of some other factor unrelated to graft failure are not included in this endpoint.

Number of HGRSAEs will be calculated for SOC patients by combining ISHLT moderate or severe PGD and primary graft failure requiring re-transplantation within the first 30 days post-transplant. HGRSAEs for the SOC patients will be compared to the DCD heart transplanted patients.

In summary, other endpoints were added, including:

- Patient and graft survival at 30 days post-transplant for SOC patients.
- Patient and graft survival at 30 days or initial hospital discharge, if later than 30 days for SOC patients.
- ISHLT moderate-severe PGD (left or right ventricle) (not including rejection or cardiac tamponade) within 24 hours according to ISHLT consensus manuscript (as defined in Appendix 1 of the protocol) for both OCS and SOC patients.
- ISHLT severe PGD (left or right ventricle) (not including rejection or cardiac tamponade) within 24 hours according to ISHLT consensus manuscript (as defined in Appendix 1 of the protocol) for SOC patients.
- HGRSAEs for SOC patients, consisting of ISHLT moderate or severe PGD and primary graft failure requiring re-transplantation within 30 days post-transplant.
- Kaplan-Meier estimated patient and graft survival at 30, 180, and 365 days post-transplant for both OCS and SOC patients.

A site poolability analysis for the primary efficacy endpoint was added for the DCD/SOC Heart Transplanted Recipient Population and for the DCD-mITT/SOC m-ITT Heart Transplanted Recipient Population.

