  class trt01a (ref='DCD');
  model survival=trt01a riskfactors / dist=binomial link=identity;
  lsmeans trt01a / diff cl alpha=0.1;
run;

data diffss;
  set diffss;
  pvalue=put(probnorm((estimate - 0.20)/stderr), 6.4));
run;
```

Per FDA's request, a sensitivity analysis will be performed to compare the DCD Heart Possible Population vs the SOC Only Population, i.e. (DCD + SOC2) vs SOC1. Also at FDA's request, an additional sensitivity analysis will repeat the primary effectiveness analysis with the same non-inferiority margin but without adjustment for covariates. Finally, assuming the primary analysis results demonstrate non-inferiority of OCS to SOC, a tipping point analysis (without risk factor adjustment) will be performed using the Wald method, in which SOC subjects categorized as having an unsuccessful 6-month survival outcome will be iteratively imputed as having a successful survival outcome. The "tipping point" is the number of SOC subjects needed to be imputed as having successful outcomes in order to no longer reject the null hypothesis of inferiority.

An additional analysis of the primary endpoint will evaluate pooling by recipient investigational site. This analysis will be performed on observed data for both the DCD/SOC Heart Transplanted Recipient Populations and the DCD/SOC-mITT Heart Transplanted Recipient Populations. A logistic regression model will be fit with all terms included in the primary effectiveness analysis, site, and the interaction of site with treatment. The p-values for site and the treatment by site interaction term in the model will be presented, with statistical significance defined at the  $\alpha = 0.15$  level. Sites with  $\leq 10$  subjects will be pooled for this analysis.

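### With about 20 expected deaths, the Wald site and treatment-by-site tests do not deliver their stated 0.15 level once five or more site categories remain, so a non-significant result is uninformative

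*SAP*

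**What the plan says.** SAP 5.5 tests site and treatment-by-site by logistic regression: "The Wald Type III p-value for site and the treatment by site interaction term will be presented". SAP 12.1 gives the model: "A logistic regression model will be fit with all terms included in the primary effectiveness analysis, site, and the interaction of site with treatment". It sets significance at 0.15 and says that sites with ten or fewer "subjects will be pooled for this analysis". SAP 3.5 gives the purpose: "A site poolability analysis for the primary efficacy endpoint was added".

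On size, SAP 5.5 says "Subjects will be recruited from up to 25 sites", and SAP 3.5 refers to the "90 DCD and 90 SOC subjects that were prospectively enrolled". Neither document gives the number of sites that enrolled or the recipients per site. SAP 3.4 assumes six-month survival of 93% (SOC) and 85% (DCD).

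Three further facts matter:

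- SAP 12.1 drops variables that stop the primary model converging and names separation as an example. It does not say whether this rule also covers the site model.
- The SAP list of tables includes survival by site (2.1.5.1 and 2.1.5.2). The shells are not shown.
- No consequence is attached to a significant or non-significant site result.

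**The concern.** A Wald test in logistic regression fails when a cell has no events. The fitted log-odds for that cell runs towards minus infinity, its standard error grows faster still, and the cell stops contributing to the statistic. Splitting about 20 deaths by site and arm makes such cells likely.

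Differences between sites are a real question here. Protocol 1.1 says DCD hearts are not used for adult heart transplantation in the U.S., and Protocol 9 asks for only one or two training runs per investigator. A p-value set against 0.15 under a poolability label invites the reader to take non-significance as reassurance. If the test almost never rejects whether or not sites differ, it gives none.

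**Working it through.** **Planning figures.** The SAP gives no operating characteristics for the site test, so the primary sample size was reproduced to confirm the rates. With unpooled variance, n = (1.645 + 0.842)² × (0.93×0.07 + 0.85×0.15) / (0.20 − 0.08)² = 6.183 × 0.1926 / 0.0144 = 82.7, or 83 per group. The SAP states 84.

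**Deaths.** 0.07×90 + 0.15×90 = 6.3 + 13.5 = 19.8.

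**Cells without deaths.** With K equal categories of n = 90/K recipients per arm, P(every cell has a death) = [(1 − 0.85ⁿ)(1 − 0.93ⁿ)]ᴷ. For K = 6, n = 15: [(1 − 0.0874)(1 − 0.3367)]⁶ = 0.6053⁶ = 4.9%. With whole-number site sizes:

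| Categories | P(no empty cell) | Expected empty cells |
|---|---|---|
| 4 | 38% | 0.89 of 8 |
| 5 | 16% | 1.62 of 10 |
| 6 | 4.9% | 2.54 of 12 |
| 8 | 0.2% | 4.83 of 16 |
| 10 | about 0% | 7.52 of 20 |

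**Mechanism.** Leaving covariates aside, the joint Wald interaction statistic is Σ wₖ(θₖ − θ̄)². Here θₖ is the log odds ratio in category k, θ̄ is the mean weighted by wₖ, and 1/wₖ is the sum of reciprocals of the four cell counts. A zero count makes wₖ zero, so that category drops out, yet the reference distribution keeps K − 1 degrees of freedom. At K = 6, on average only 6 × 0.6053 = 3.6 categories contribute, against 5 degrees of freedom. The categories that drop out include those with no deaths, which are part of the evidence of heterogeneity.

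**Simulation with fixed categories.** 90 + 90 recipients, SOC mortality 7% everywhere, 600 to 1,000 trials per scenario (400 to 600 for the permutation test), tests at 0.15. Percentages of trials rejecting; *either Wald* means site or interaction:

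| Categories (recipients per arm in each) | DCD mortality | Wald interaction | Either Wald | Likelihood-ratio interaction | Permutation, DCD deaths |
|---|---|---|---|---|---|
| 2 (45, 45) | 15% in all | 13.1 | 22.6 | 19.8 | 8.8 |
| 2 | 25% / 5% | 48.1 | 70.3 | 62.2 | 86.5 |
| 3 (30 each) | 15% in all | 5.8 | 10.2 | 21.8 | 13.0 |
| 3 | 35% / 5% / 5% | 36.8 | 56.8 | 71.5 | 94.0 |
| 4 (40, 25, 15, 10) | 15% in all | 0.8 | 3.1 | 20.8 | 14.0 |
| 4 | largest 30%, rest 5% | 9.7 | 13.6 | 60.6 | 89.5 |
| 6 (30, 20, 15, 10, 8, 7) | 15% in all | 0.0 | 0.6 | 22.7 | 19.8 |
| 6 | largest 30%, rest 5% | 0.4 | 0.7 | 51.8 | 82.5 |
| 6 | last two 50%, rest 5% | 0.8 | 15.7 | 75.8 | 98.3 |
| 8 (25, 18, 12, 9, 7, 7, 6, 6) | 15% in all | 0.0 | 0.0 | 17.0 | 15.3 |
| 8 | largest 30%, rest 5% | 0.0 | 0.0 | 39.2 | 76.0 |
| 8 | last two 50%, rest 5% | 0.0 | 3.1 | 63.0 | 94.3 |

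With five equal categories the Wald interaction test rejects in 0.1 to 0.4% under no difference. With 40% against 0% DCD mortality, neither Wald test rejects. Adding four null binary covariates, with 40% DCD mortality in a third of sites and 3% elsewhere, gives *either Wald* 2.7% at six categories and 0.7% at eight. Across all scenarios the likelihood-ratio test rejects in 15 to 27% under no difference. The permutation test shows 9 to 20%. Its simulation standard error is about √(0.15×0.85/400) = 1.8 points at 400 trials, and with two categories discreteness pulls it below 15%.

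**Simulation with the pooling rule.** With 10 to 25 sites of uneven size and sites of ten or fewer pooled together, about 6 to 9 categories remain on average. An empty cell occurs in 97 to 100% of trials. The Wald interaction test rejects in 0 to 0.3% under no difference, and in 0 to 0.8% when half the sites have 27% DCD mortality and half 3%.

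**Limiting case.** 180/25 = 7.2 recipients per site. If no site exceeds ten and small sites form one category, there is no site term to test.

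**The case against.** A reader might infer that large site differences would be reported as poolable, or that the non-inferiority result is at risk. The documents support neither reading. The SAP only presents p-values against 0.15, with no rule for what follows, and the primary estimate in SAP 12.1 is not conditional on them. This is a supplementary check that the protocol did not contain.

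A reader might also infer that pooling small sites causes the empty cells. It does the reverse. Unpooled, 25 sites make 50 site-by-arm cells, and 20 deaths leave at least 30 of them empty. Pooling fills cells; its cost is that it dilutes differences between the pooled sites.

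Other objections stand in part:

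- The failure depends on enrolment. With two or three categories, either Wald test finds the large differences examined in 52 to 70% of trials; with four, usually in 10 to 58%, but in only 0.2 to 0.3% when two of the four have no DCD deaths.
- The rule for dropping variables might apply. The interaction would then often go untested, which is no more informative.
- The by-site tables may already show deaths and numbers by arm.
- A permutation test is not powerful either. Over unpooled sites, with 27% against 3% DCD mortality, it rejected in 33 to 44% in one set of runs (20 and 25 sites) and in 52 to 71% in another that tested DCD deaths only. It ignores the risk factors and does not test interaction.

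None of this restores the stated level of the Wald tests.

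**Conclusion.** The point holds, on condition that about five or more site categories remain after pooling. That is plausible for 180 recipients at up to 25 sites, but it is an assumption. The Wald interaction test then rejects in about 0 to 0.4% of trials under no difference instead of 15%. Under most large DCD differences the Wald tests reject in about 0 to 3%. The exceptions found were 8% and 16%, both with six unequal categories of which two had 50% DCD mortality; five categories is the border, where extreme differences may be seen more often. The results also rest on the SAP's planned mortality rates. A non-significant result would say almost nothing about site differences. The consequence is confined to this check and how it is read; the primary analysis is unaffected.

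**What to change.** In SAP 5.5 and 12.1:

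1. Replace the Wald p-values with a within-arm permutation (exact) test of deaths across unpooled sites. Label it as a test of site heterogeneity within each arm, not of interaction.
2. If an interaction p-value from the logistic model is kept, calibrate it, for example by permutation or parametric bootstrap of the likelihood-ratio statistic. The plain likelihood-ratio test is not enough: it rejects in up to about 21 to 27% under no difference.
3. State whether the rule for dropping non-converging variables applies to the site model.
4. Show deaths and numbers by site and arm in Tables 2.1.5.1 and 2.1.5.2, if the shells do not already.
5. State that a non-significant p-value is not evidence of poolability.

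The cost is SAP wording and some code. The downside is that a test that holds its level will flag sites by chance about 15% of the time, and power stays limited by about 20 deaths.

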## **5.6 Multiple Comparisons / Multiplicity**

No adjustments for multiple comparisons/multiplicity will be made.

## **5.7 Examination of Subgroups**

Subgroup analyses of the survival and PGD endpoints for the DCD /DCD-mITT Heart Transplanted Recipient Population will be performed based on the following WIT subgroups: 0 to 20 minutes; >20 to 30 minutes; and >30 minutes.

## 6.0 ANALYSIS POPULATIONS

The **DCD Heart Transplanted Recipient Population** will consist of all eligible recipients who were randomized and transplanted with an eligible DCD donor heart that met the warm ischemic time (WIT) limit (WIT  $\leq$  30 mins), preserved on OCS and met all transplantability criteria. Recipients transplanted with a pediatric donor heart will be excluded from this analysis population as these donor hearts do not meet eligibility criteria for the trial.

WIT is defined as time from when mean systolic blood pressure (SBP) is  $<$  50 mmHg or peripheral saturation  $<$  70%, whichever occurs first, to aortic cross-clamp and administration of cold cardioplegia in the donor.

The **DCD modified Intent-to-Treat (DCD-mITT) Heart Transplanted Recipient Population** will include all recipients who were randomized and transplanted with a DCD donor heart that was instrumented on the OCS Heart System.

The **SOC Heart Transplanted Recipient Population** will consist of all recipients who received a standard criteria donor heart (**SOC1 + SOC2** as defined in **Section 3.2**), excluding recipients transplanted with a pediatric donor heart.

The **SOC modified Intent-to-Treat (SOC-mITT) Heart Transplanted Recipient Population** will consist of all recipients who received a standard criteria donor heart (**SOC1 + SOC2**).

The **OCS Heart Population** will consist of all randomized DCD donor hearts that were instrumented on the OCS Heart System without protocol deviations. Donor hearts with warm ischemic time  $>$  30 mins or from pediatric donors will be excluded. The primary analysis of utilization rate will be based on the OCS Heart Population.

The **modified OCS (mOCS) Heart Population** will consist of all randomized DCD donor hearts that were instrumented on the OCS Heart System. The DCD donor heart utilization rate will also be calculated based on this modified OCS Heart Population.

The **DCD Heart Possible Population** will consist of all eligible recipients who are randomized to the DCD Heart Possible group and receive either a DCD heart preserved on OCS or an SOC donor heart.

The **SOC Heart Only Population** will consist of all eligible recipients who are randomized to the SOC Heart Only group and receive a SOC heart.

After completing enrollment there were 6 cases in which a SOC donor heart was transplanted without randomization. Since those 6 patients were transplanted without randomization, they will be excluded from any analysis populations.

